18.3 QoL Algorithm

18.3.1 NTDT-PRO (Non-Transfusion-Dependent Thalassemia Patient-Reported Outcome)

The NTDT-PRO is a disease-specific QoL tool used to assess the severity of symptoms associated with NTDT β -thalassemia. It is administered as a daily eDiary with recall of thalassemia-related symptoms during the past 24 hours.

Baseline and post-baseline score calculations are performed based on weekly item scores. Baseline scores are calculated over 7 days prior to Dose 1 Day 1. The NTDT-PRO scores are recorded daily from Dose 1 Day 1 through Week 24. After Week 24, the NTDT-PRO scores are recorded by visit. The Week 1 weekly scores are calculated from Day 1 to Day 7. The Week 2 weekly scores are calculated from Day 8 to Day 14, similarly through the Week 24 weekly scores. After Week 24, the weekly scores will be derived over 7 days based on the closest visit day.

Step 1: Scoring the Items

All items have score ranges from 0–10, with higher scores indicating more severe symptoms. If entries are missing for ≥ 4 days in any week, the average weekly item score is declared as missing. Otherwise the mean of the non-missing item values is taken.

If subjects do not have any valid NTDT-PRO scores at baseline, Week 13-24 or Week 37-48 due to the minimum 4-day non-missing weekly score requirement, the 4-day non-missing rule will be relaxed to at least 2 days to avoid missing data. The justification of this relaxed rule is supported by the simulation results showing that no significant difference is found between 4-day and 2-day non-missing weekly scores (*Psychometric assessment of the NTDT-PRO using data from the phase 2 luspatercept study, 2020*).

Step 2: Calculating Scores for the T/W Domain

The average of non-missing weekly item scores from the first 4 items (i.e., TiredNA, TiredPA, WeakNA, WeakPA) will be calculated if at least 1 non-missing weekly item score for tiredness [i.e. TiredNA, TiredPA] and at least 1 non-missing weekly item score for weakness [i.e. WeakNA, WeakPA]; otherwise, the weekly T/W score will be set to missing. Thus, the range of weekly T/W score is 0–10.

Step 3: Calculating Scores for the SoB Domain

The average of non-missing weekly item scores from the last 2 items (i.e., SobNA and SobPA) will be calculated if $\geq 50\%$ of the items (≥ 1 items) are not missing; otherwise, the weekly SoB score will be set to missing. Thus, the range of weekly SoB score is 0–10.

NTDT-PRO© (version 2) Instrument

For each of the following questions, please choose the number that best describes the symptoms that you may have experienced during the **past 24 hours**.

1. How would you rate your tiredness (lack of energy) when you were not doing physical activity during the past 24 hours?

0 1 2 3 4 5 6 7 8 9 10

No tiredness Extreme tiredness

2. How would you rate your tiredness (lack of energy) when you were doing physical activity during the past 24 hours?

0 1 2 3 4 5 6 7 8 9 10

No tiredness Extreme tiredness

3. How would you rate your weakness (lack of strength) when you were not doing physical activity during the past 24 hours?

0 1 2 3 4 5 6 7 8 9 10

No weakness Extreme weakness

4. How would you rate your weakness (lack of strength) when you were doing physical activity during the past 24 hours?

0 1 2 3 4 5 6 7 8 9 10

No weakness Extreme weakness

5. How would you rate your shortness of breath when you were not doing physical activity during the past 24 hours?

 0 1 2 3 4 5 6 7 8 9 10

No
shortness
of breath

Extreme
shortness
of breath

6. How would you rate your shortness of breath when you were doing physical activity during the past 24 hours?

 0 1 2 3 4 5 6 7 8 9 10

No
shortness
of breath

Extreme
shortness
of breath

For validation purposes only

7. During the past 24 hours, how would you rate the overall severity of your thalassemia symptoms?

 0 1 2 3 4 5 6 7 8 9 10

No
symptoms

Very
severe
symptoms

For validation purposes only (administered once every 3 weeks):

8. How would you rate the overall change in your thalassemia symptoms since the start of this study?

- A great deal better
- Much better
- A little better
- No change
- A little worse
- Much worse
- A great deal worse

18.3.2 FACIT-F

FACIT-F evaluation include FACT-G scale and FACIT Fatigue Subscale (FS). FACT-G scale are based on 4 domains: Physical Well-Being (PWB), Social/Family Well-Being (SWB), Emotional Well-Being (EWB), and Functional Well-Being (FWB). In ERT system, the questions of Fatigue scale were in the section of Additional Concern. The version 4 of FACIT-F was applied in the study.

Domain	Questions
PWB	1, 2, 3, 4, 5, 6, 7
SWB	8, 9, 10, 11, 12, 13, 14
EWB	15, 16, 17, 18, 19, 20
FWB	21, 22, 23, 24, 25, 26, 27
FS	28, 29, 30, 31, 32, 33, 34, 35, 36, 37, 38, 39, 40

The 5 domain scores and the total score are obtained by the following steps:

Step 1: Score the Individual Question

All questions have score range 0-4 as collected and higher score indicates better QoL. So some of item response, ie raw collection need be reversed by subtracting 4 to obtain the item score. The score will be reversed from response for following questions:

Domain	Questions
PWB	1, 2, 3, 4, 5, 6, 7
EWB	15, 17, 18, 19, 20
FS	28, 29, 30, 31, 32, 33, 36, 37, 38, 39, 40

For the other questions, the response is the question score.

Step 2: Calculating Domain Score

If more than 80% of the total questions in the domain are answered, the domain score will be calculated as

$$\frac{\text{Sum of item score in the domain}}{\text{Number of items answered in the domain}} \times \text{Number of items in domain}$$

Otherwise, it will be left as missing.

Step 3: Calculating Total Score

If all domain scores are derived, the total score is the sum of all domain scores

$$\text{FACIT-F Total Score} = \text{PWB score} + \text{SWB score} + \text{EWB score} + \text{FWB score} + \text{FS score}$$

Otherwise, it will be left as missing.

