- SF-36 v2 – The SF-36 version 2 is a 36-item generic PRO questionnaire used to assess patient-reported HR-QoL outcomes. The SF-36 yields scores for eight domains of health: Physical Functioning (PF), Role-Physical (RP), Bodily Pain (BP), General Health (GH), Vitality (VT), Social Functioning (SF), Role Emotional (RE), and Mental Health (MH) as well as physical component summary (PCS) and mental component summary (MCS) scores. The SF-36 is scored such that higher scores reflect a better health state. For this study, a 7-day recall period is used.

Subjects will be asked to complete this quality of life questionnaire at Screening and every other dose (at Dose 1 Day 1, Dose 3 Day 1, Dose 5 Day 1 and thereafter) in the DBTP and at 9 weeks after last dose, as detailed in [Table 3](#). The questionnaire must be always completed by the subjects before knowing the predose Hb test result. In the OLP, subjects will complete this quality of life questionnaire every other dose as detailed in [Table 3](#).

- FACIT-F – The FACIT-Fatigue, is a multidimensional, self-report quality of life instrument. It consists of 27 core items, the Functional Assessment of Cancer Therapy - General (FACT-G) questionnaire, which assesses patient function in 4 domains: Physical, Social/Family, Emotional, and Functional well-being, which is further supplemented by a 13-item measure designed to capture cancer-related fatigue, the Fatigue subscale (FS). The items are measured on a response scale with five options (0 = not at all to 4 = very much) and has a 7-day recall period.

Subjects will be asked to complete this quality of life questionnaire at Screening and every other dose (at Dose 1 Day 1, Dose 3 Day 1, Dose 5 Day 1, and thereafter) in the DBTP and at 9 weeks after last dose, as detailed in [Table 3](#). In the OLP, subjects will complete this quality of life questionnaire every other dose as detailed in [Table 3](#). The questionnaire must be always completed by the subjects before knowing the predose Hb test result.

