Mean NTDI-PRO (T/W domain) change from baseline over a 12-week interval between Weeks 37 to 48 (nominal Dose 13 to Dose 17) will be analyzed using ANCOVA method with treatment group and randomization stratification factor(s) in the model as covariates.

The treatment-by-stratification-factor(s) interaction will be added to the ANCOVA model as a sensitivity analysis and results from this model will be compared to the primary fixed effects model (without the interaction effect). If the interaction is significant at a 2-sided 0.1-alpha level, the nature of this interaction will be inspected as to whether it is quantitative (that is, the treatment effect is consistent in direction but not in size of effect) or qualitative (the treatment is beneficial in some values of the stratification factor(s)). If the interaction effect is found to be quantitative, results from the primary fixed effect model will be presented. If the interaction effect is found to be qualitative, further inspection will be used to identify in what values of the stratification factor(s) the treatment is more beneficial.

10.4.5 FACIT-F Fatigue Subscale (FS) Response at Weeks 13 to 24 and Weeks 37 to 48

Proportion of subjects with an increase from baseline ≥ 3 in mean FACIT-F FS score, over Weeks 13 to 24 in the luspatercept group will be compared with the placebo group. The CMH test will be used with baseline FACIT-F FS category ≥ 37 versus < 37 as the stratum to compare the response rates between the 2 groups. The selection of 37 as a threshold is based on a Phase 2 Luspatercept study (A536-06) in which it corresponds to a NTDI-PRO T/W domain scores of 4. The corresponding 95% confidence interval for odds ratio will also be provided. Similar analysis will be performed for Weeks 37 to 48.

10.4.6 SF-36 v2: Mean Change from Baseline at Week 24 and Week 48

The SF-36 Version 2.0 (acute condition with 1-week recall period) is a self-administered instrument consisting of 8 multi-item scales that assess 8 health domains: Physical functioning (PF), Role-Physical (RP), Bodily Pain (BP), General Health (GH), Vitality (VT), Social functioning (SF), Role-Emotional (RE), and Mental Health (MH). Two overall summary scores, Physical Component Summary (PCS) and Mental Component Summary (MCS), will be calculated from the 8 health domains. The primary interests of the SF-36 are the PCS and MCS norm-based scores.

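### The FACIT-F key in SAP 18.3.2 describes reversal as subtracting 4, which reverses nothing if taken literally; it is most likely a wording slip, and one line repairs it

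*SAP*

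**What the plan says.** Protocol 6.8 describes the raw FACIT-F responses: "The items are measured on a response scale with five options (0 = not at all to 4 = very much").

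SAP 18.3.2, Step 1, states the target scale, "All questions have score range 0-4 as collected and higher score indicates better QoL", and then how to reach it for items worded the other way: "raw collection need be reversed by subtracting 4 to obtain the item score". The Fatigue Subscale consists of questions "28, 29, 30, 31, 32, 33, 34, 35, 36, 37, 38, 39, 40"; those to be reversed are "28, 29, 30, 31, 32, 33, 36, 37, 38, 39, 40". That leaves 34 and 35, which fall under "For the other questions, the response is the question score". Seven Physical Well-Being and five Emotional Well-Being questions are also on the reversal list.

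Step 2 prorates a domain score "If more than 80% of the total questions in the domain are answered".

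The Fatigue Subscale is then used as follows:

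- Mean change over Weeks 13 to 24 and Weeks 37 to 48 (SAP 4.2.2.2, 10.4.1).
- Response, meaning a rise of 3 points or more, over the same two intervals. The CMH test is stratified by baseline score at 37 (SAP 10.4.5; Protocol 9.6.3.6). SAP 10.4.5 explains the cut-off: "The selection of 37 as a threshold is based on a Phase 2 Luspatercept study".
- A subgroup split of the baseline score at 43 (SAP 10.5).

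**The concern.** A scoring appendix should let a programmer derive the score without guessing. Here the stated operation does not do what the sentence says it does. Subtracting a constant shifts a scale; it cannot reverse it. If the phrase were programmed as it stands, the direction would be wrong on 11 of the 13 Fatigue Subscale items. The 3-point response rule would then credit worsening on those items, and the stratum at 37 and the subgroup at 43 would each hold all subjects in one level.

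No other section supplies the right formula. For the SF-36, by contrast, SAP 18.3.3 writes the reversal out value by value and SAP 10.4.6 names scoring software. For FACIT-F the SAP names the instrument version but no scoring software or manual.

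**Working it through.** **Inputs.** Raw responses 0 to 4 (Protocol 6.8). Fatigue Subscale: 13 questions, 28 to 40, of which 11 are reversed and 2 (34 and 35) keep the raw response. Domain score = (sum of item scores / items answered) × 13. Cut-offs 37 and 43; response threshold +3.

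**Items affected.** 7 (Physical) + 5 (Emotional) + 11 (Fatigue) = 23 of 40.

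**Single item.** Responses 0, 1, 2, 3, 4 become:

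- response − 4: −4, −3, −2, −1, 0 (order unchanged, outside 0 to 4 except at the top);
- 4 − response: 4, 3, 2, 1, 0 (order reversed, inside 0 to 4).

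**Can the plan's cut-offs be reproduced?** With all 13 items answered:

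| Response pattern | response − 4 | 4 − response |
|---|---|---|
| Worst fatigue: 4 on the 11 items, 0 on 34 and 35 | 11×0 + 2×0 = 0 | 11×0 + 2×0 = 0 |
| Best: 0 on the 11 items, 4 on 34 and 35 | 11×(−4) + 2×4 = −36 | 11×4 + 2×4 = 52 |
| Lowest attainable | 11×(−4) + 0 = −44 | 0 |
| Highest attainable | 0 + 2×4 = 8 | 52 |

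Under 4 − response, 37 and 43 both lie inside 0 to 52. Under response − 4, neither can be reached.

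**With prorating.** 0.80 × 13 = 10.4, so at least 11 items are needed. The highest literal score with 11 answered has nine reversed items at response 4 (score 0 each) and items 34 and 35 at 4: 8/11 × 13 = 9.45. With 12 answered it is 8/12 × 13 = 8.67. Both remain far below 37. Under 4 − response, prorating leaves the range at 0 to 52.

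**Direction of change.** Let R be the raw sum on the 11 reversed items and P the raw sum on items 34 and 35, with all items answered.

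- Literal: score = P + R − 44, so change = ΔP + ΔR.
- 4 − response: score = P + 44 − R, so change = ΔP − ΔR.

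Example: every response is 2, then three reversed items improve by one category (ΔR = −3, ΔP = 0).

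- Literal: 11×(−2) + 4 = −18, moving to −21, a change of −3.
- 4 − response: 11×2 + 4 = 26, moving to 29, a change of +3, which meets the response threshold.

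A literal score is positive only if P + R exceeds 44. Since P is at most 8, R must exceed 36 out of 44, which means near-worst answers on the reversed items. Most literal scores would therefore be negative.

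**Other domains, literal key.** Physical Well-Being: 7×(−4) = −28 to 0. Emotional Well-Being: 5×(−4) = −20 to 4, the one unreversed item supplying the 4.

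**The case against.** The strongest reply is that the paragraph settles its own meaning. It gives a 0 to 4 range, says which direction is better, and twice calls the operation a reversal. Only the phrase about subtracting 4 points elsewhere, and subtracting the response from 4 satisfies everything else. The response rule, the cut-off of 37 carried over from an earlier luspatercept study, and the cut-off of 43 all fit that reading and no other. A literal implementation would produce mostly negative scores, an empty upper stratum and an empty upper subgroup, which ordinary checking should catch. There is also a separate HRQoL SAP (SAP 10.4.6 and 14), which is not available here, so 18.3.2 may not be the only specification.

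Most of this stands, and it limits the point. It does not remove it. The sentence is the only reversal rule given for FACIT-F, it is operative text for protocol endpoints, and it is wrong as it stands. The existence of another plan is no evidence that it corrects this line.

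A reader might infer that the trial's fatigue results will be inverted, or that worsening will be counted as response. The documents do not support that: it requires someone to program one phrase against the rest of its paragraph and accept visibly impossible output. Nor do they support a threat to the main conclusions. The FACIT-F endpoints are other-secondary (SAP 4.2.2.2) and lie outside the gatekeeping sequence (SAP 10.1 and 10.3).

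**Conclusion.** The point holds as a correction of a faulty scoring instruction, most likely a wording slip. Read literally, the rule leaves 23 items unreversed, 11 of them among the 13 on the Fatigue Subscale. It replaces a 0 to 52 scale by one on which worst fatigue scores 0, best scores −36, and the maximum is +8 with complete questionnaires or 9.45 with prorating at 11 items. The SAP's own stated range, direction and cut-offs all show that 4 − response was meant.

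The reach is four other-secondary endpoints (mean change and 3-point response, each over two intervals) and one of the ten subgroup factors in SAP 10.5, which is also applied to the primary and key secondary endpoints. Their overall tests do not use the Fatigue Subscale and are unaffected.

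The figures rest on the raw 0 to 4 coding in Protocol 6.8 and on the SAP's item lists as printed. Any actual harm rests on the further assumption that the phrase is programmed literally, for which the documents give no sign.

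**What to change.** In SAP 18.3.2, Step 1, replace the phrase about subtracting 4 with: item score = 4 − response for the listed questions. The Fatigue Subscale then runs from 0 to 52, with higher meaning less fatigue; stating that range in the same place is optional but gives the programmer an immediate check. If the separate HRQoL SAP carries its own FACIT-F key, confirm that it agrees.

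The cost is one line. It needs no new data and changes no endpoint, cut-off, sample size or alpha allocation.

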18.3.3 SF-36

The SF-36 is a self-administered instrument consisting of 8 multi-item scales that assess 8 health domains: (1) Physical functioning (PF), 10 items from 3a to 3j, (2) Role-Physical (RP), 4 items from 4a to 4d, (3) Bodily Pain (BP), items 7 and 8, (4) General Health (GH), items 1 and 11a to 11d, (5) Vitality (VT), items 9a, 9e, 9g, and 9i, (6) Social functioning (SF), items 6 and 10, (7) Role-Emotional (RE), items 5a, 5b, and 5c, (8) Mental Health (MH), 5 items 9b, 9c, 9d, 9f and 9h. Two summary scales, Physical Component Summary (PCS) and Mental Component Summary (MCS), will be calculated using norm-based scores from the 8 health domains. The primary interests of the SF-36 are the 8 health domain scores and the PCS and MCS scores.

The 8 health domain scores and the PCS and MCS scores are obtained by the following steps.

Step 1: Score the 8 Health Domain

All questions will be scored as per the raw data value collected with the following exceptions. Seven questions (6, 9a, 9d, 9e, 9h, 11b, and 11d) will use the reversed score, so that 5=1, 4=2, 3=3, 2=4 and 1=5. The higher individual score indicates the better health.

The SF-36 scoring system relies on an assumption of linearity among the responses. However, question 1, 7 and 8 require recalibration to satisfy this important scaling assumption.

Question 1

Q1 (verbatim responses)	Q1 (raw value)	Q1 (final response value)
Excellent	1	5.0
Very good	2	4.4
Good	3	3.4
Fair	4	2.0
Poor	5	1.0

Question 7

Q7 (verbatim responses)	Q7 (raw value)	Q7 (final response value)
None	1	6.0
Very mild	2	5.4
Mild	3	4.2
Moderate	4	3.1
Severe	5	2.2
Very severe	6	1.0

Question 8 will have its score inverted too, but also depends on the response given for question 7, in the following manner:

Q7	Q8	Q8	Q8
----	----	----	----

(raw value)	(verbatim responses)	(raw value)	(final response value)
1	Not at all	1	6
2, 3, 4, 5 or 6	Not at all	1	5
any	A little bit	2	4
any	Moderately	3	3
any	Quite a bit	4	2
any	Extremely	5	1

If question 7 is not answered then question 8 will have its score recoded to preserve linearity, in the following manner:

Q7 (raw value)	Q8 (verbatim responses)	Q8 (raw value)	Q8 (final response value)
missing	Not at all	1	6.0
missing	A little bit	2	4.75
missing	Moderately	3	3.5
missing	Quite a bit	4	2.25
missing	Extremely	5	1.0

Missing data will be handled per the SF-36 version 2 scoring guideline. If more than half of the items are answered in a multi-item domain, then the missing item(s) will be imputed as the average score of the completed items in the same domain. If no more than half of the items are answered, the missing item will be left as missing

Step 2: Calculating Domain Score and Transforming Domain Score to 0-100 Scale Score

The total raw score for each health domain scale will be computed. The total raw score is the simple algebraic sum of the final response values for all items in a given scale. The resulting total raw score for each health domain is then transformed to a 0-100 scale score:

Health Domain	Sum of final response values	Transformed 0-100 Scale Score
PF	Sum_PF=3a+3b+3c+3d+3e+3f+3g+3h+3i+3j	T_PF = ((Sum_PF-10)/40)*100
RP	Sum_RP=4a+4b+4c+4d	T_RP = ((Sum_RP - 4)/16)*100
BP	Sum_BP=7+8	T_BP = ((Sum_BP - 2)/10)*100
GH	Sum_GH=1+11a+11b+11c+11d	T_GH = ((Sum_GH - 5)/20)*100
VT	Sum_VT=9a+9e+9g+9i	T_VT = ((Sum_VT - 4)/16)*100
SF	Sum_SF=6+10	T_SF = ((Sum_SF - 2)/8)*100
RE	Sum_RE=5a+5b+5c	T_RE = ((Sum_RE - 3)/12)*100
MH	Sum_MH=9b+9c+9d+9f+9h	T_MH = ((Sum_MH - 5)/20)*100

Step 3: Computing Norm-based Domain Scores

In order for one health domain scale be meaningfully compared with those from the other scales and that domain scores have a direct interpretation in relation to the distribution of scores in U.S. general population, the 0-100 scale score for each health domain will be converted to norm-based scores using a T-score transformation and higher norm-based score indicates better health:

Health Domain	Transformation of 0-100 scores to z-scores	Transformation of z-scores to norm-based scores
PF	$Z_{PF} = (T_{PF} - 83.29094)/23.75883$	$N_{PF} = 50 + (Z_{PF}*10)$
RP	$Z_{RP} = (T_{RP} - 82.50964)/25.52028$	$N_{RP} = 50 + (Z_{RP}*10)$
BP	$Z_{BP} = (T_{BP} - 71.32527)/23.66224$	$N_{BP} = 50 + (Z_{BP}*10)$
GH	$Z_{GH} = (T_{GH} - 70.84570)/20.97821$	$N_{GH} = 50 + (Z_{GH}*10)$
VT	$Z_{VT} = (T_{VT} - 58.31411)/20.01923$	$N_{VT} = 50 + (Z_{VT}*10)$
SF	$Z_{SF} = (T_{SF} - 84.30250)/22.91921$	$N_{SF} = 50 + (Z_{SF}*10)$
RE	$Z_{RE} = (T_{RE} - 87.39733)/21.43778$	$N_{RE} = 50 + (Z_{RE}*10)$
MH	$Z_{MH} = (T_{MH} - 74.98685)/17.75604$	$N_{MH} = 50 + (Z_{MH}*10)$

Step 4: Computing the Aggregated Physical and Mental Component Scores

Using the standardized domain scores (z-scores), aggregated PCS and MCS score will be computed based on the weights from the U.S. general population:

$$\text{Aggregate PCS score} = (Z_{PF} * 0.42402) + (Z_{RP} * 0.35119) + (Z_{BP} * 0.31754) + (Z_{GH} * 0.24954) + (Z_{VT} * 0.02877) + (Z_{SF} * -.00753) + (Z_{RE} * -.19206) + (Z_{MH} * -.22069)$$

$$\text{Aggregate MCS score} = (Z_{PF} * -0.22999) + (Z_{RP} * -0.12329) + (Z_{BP} * -0.09731) + (Z_{GH} * -0.01571) + (Z_{VT} * 0.23534) + (Z_{SF} * 0.26876) + (Z_{RE} * -.43407) + (Z_{MH} * 0.48581)$$

Step 5: Calculating the Norm-based PCS and MCS scores:

Aggregate PCS and MCS scores are standardized using a linear T-score transformation with a mean of 50 and a standard deviation of 10 and higher component score indicates better health:

$$\text{Norm-based PCS} = 50 + (\text{Aggregate PC score} * 10)$$

$$\text{Norm-based MCS} = 50 + (\text{Aggregate MC score} * 10)$$

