Scores for each domain and composite summary scale of the SF-36 will be derived using the Quality Metric's Health Outcomes™ Scoring Software 5.1, a software designed to provide standardized scoring methods for the SF-36 based on the 2009 US general population normative data (*Maruish, 2011*). The scoring algorithm, using the 1998 US general population normative data as an example, for the SF-36 is shown in Appendix 18.3.3.

Summary statistics (n, mean, median, SD, range) for PCS and MCS norm-based scores along with the change from baseline will be summarized at Weeks 12, 24, 36, and 48 for each treatment group. The Norm-base scores will be used for domain analysis and the PCS analysis. The raw scores for each individual question and the calculated domain and component scores will be presented in the listings for SF-36.

A mixed effect repeated measure model will be used with intercept and time as the random effect. The model includes the change from baseline scores up to Week 48 as the outcome, and treatment group assignment, time (weeks since Dose 1 Day 1), baseline scores, randomization stratification factor(s), time-by-baseline score, and time-by-treatment group assignment terms in the model. The unstructured covariance matrix will be used to obtain the random effects variance components.

If the MMRM model using an unstructured covariance matrix fails to converge with the default Newton-Raphson algorithm, the Fisher scoring algorithm or another appropriate method will be used to provide initial values of the covariance parameters. In the rare event that none of the above methods yields convergence, a structured covariance, such as heterogeneous Toeplitz and Toeplitz structures, will be used to model the correlation among repeated measurements. In this case, the empirical option will be used because the sandwich variance-covariance estimator is asymptotically consistent.

To assess the extent of missing data at each assessment visit by treatment group, compliance rates for the SF-36 will be estimated on the ITT population separately based on the number of subjects included in the ITT population per treatment group who are eligible for assessment at a given scheduled visit. Subjects will be considered compliant with completion of the SF-36 assessment if at least half of the 36 items (i.e., ≥ 18 items) are completed.

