10.6.2 Missing Data for QoL Assessment

For continuous and categorical QoL assessments, the complete case analysis is used for the primary analysis. For the key secondary endpoint, NTDT-PRO T/W domain score at Week 13-24, the supportive/sensitivity analysis will use the postbaseline mean imputation, the baseline imputation or multiple imputation (MI) methods to assess the robustness of the primary result.

To assess the extent of missing data at each assessment visit by treatment group, compliance rates for the NTDT-PRO, FACIT-F, and SF-36 assessments at each scheduled visit will be provided. The compliance rate for each assessment at each visit is defined as follows:

- NTDT-PRO: The number of subjects with at least half of 6 weekly item scores for that week being non-missing (i.e., ≥ 3 items) divided by the number of ITT subjects who are still expected to provide PRO assessment at that time point.
- FACIT-F: The number of subjects with at least 80% of the 40 items (i.e., ≥ 32 items) for that visit being completed divided by the number of ITT subjects who are still expected to provide FACIT-F assessment at that time point.
- SF-36: The number of subjects with at least 50% of the 36 items (i.e., ≥ 18 items) for that visit being completed divided by the number of ITT subjects who are still expected to provide SF-36 assessment at that time point.

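### SAP 18.3.3 contradicts itself on the two-item Bodily Pain scale: it recodes question 8 for use when question 7 is missing, but its more-than-half rule means the recode can never enter a score

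*SAP*

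**What the plan says.** SAP 18.3.3 builds the SF-36 scores in five steps.

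- **Step 1, recode.** Bodily Pain (BP) consists of questions 7 and 8. For a missing question 7 the SAP states: "If question 7 is not answered then question 8 will have its score recoded to preserve linearity". A table then turns raw answers 1 to 5 into 6.0, 4.75, 3.5, 2.25 and 1.0.
- **Step 1, missing items.** "If more than half of the items are answered in a multi-item domain, then the missing item(s) will be imputed", using the average of the completed items in that domain. The complement is also written out: "If no more than half of the items are answered, the missing item will be left as missing".
- **Step 2.** "The total raw score is the simple algebraic sum of the final response values for all items in a given scale". For BP that is question 7 plus question 8.
- **Step 4.** PCS and MCS are each a weighted sum of all eight domain z-scores. BP has weight 0.31754 in PCS and -0.09731 in MCS. No rule is given for a missing domain.

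The body of the SAP (10.4.6) names a different operative tool: "Scores for each domain and composite summary scale of the SF-36 will be derived using the Quality Metric's Health Outcomes™ Scoring Software 5.1". That section uses 2009 US norms and presents the appendix algorithm with 1998 norms as an example. The missing-data paragraph of 18.3.3 opens by deferring to the SF-36 version 2 scoring guideline, and protocol 9.6.3.7 defers to the instrument developers' directions. Neither source is reproduced.

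**The concern.** Two instructions in one section cannot both be meant. A recode for a lone question 8 presupposes that one answered item is enough to score BP. The missing-item rule says that it is not. A programmer following the appendix would write the recode and never see it reach a scale score.

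Change in PCS and MCS at Weeks 24 and 48 is a listed secondary endpoint (SAP 4.2.2.2), and the appendix holds the only item-level SF-36 rule that the documents spell out. If it is applied, or used to check the vendor's output, visits with one unanswered item in a two-item scale have no summary score, although almost everything else was answered.

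**Working it through.** **1. Reproduce the SAP's own recode.** Stretch raw question 8 (1 to 5) linearly over question 7's final range (1 to 6), with high meaning less pain: value = 6 - 1.25 × (raw - 1). This gives 6.0, 4.75, 3.5, 2.25 and 1.0, an exact match.

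**2. What the recode is for.** If question 7 is replaced by the recoded question 8, Sum_BP = 2 × value = 12, 9.5, 7, 4.5 or 2. By Step 2, T_BP = (Sum_BP - 2)/10 × 100 = 100, 75, 50, 25 or 0, the full scale in equal steps. With unrecoded values of 5 to 1, T_BP would be 80, 60, 40, 20 or 0 and could not reach the top. The recode therefore makes sense as preparation for scoring BP from question 8 alone.

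**3. Apply the written rule.** One of two items answered is 1/2 = 0.50, which is not more than half. Question 7 stays missing, Sum_BP cannot be formed, and neither can Z_BP, PCS or MCS. With both items answered, the recode does not apply. So it never enters a score.

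**4. Which scales the wording touches.** Minimum answered items, from the item lists in 18.3.3:

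| Scale | Items | More than half | At least half |
|---|---|---|---|
| PF | 10 | 6 | 5 |
| RP | 4 | 3 | 2 |
| BP | 2 | 2 | 1 |
| GH | 5 | 3 | 3 |
| VT | 4 | 3 | 2 |
| SF | 2 | 2 | 1 |
| RE | 3 | 2 | 2 |
| MH | 5 | 3 | 3 |

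Five scales differ. Only in BP and Social Functioning (SF) does a single missing item decide the matter.

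**5. Possible size if the appendix governs.** The documents give no item non-response rate, so a rate p of 0.2% to 2%, independent across items, is assumed. The share of questionnaires with at least one unscorable scale, and hence no PCS or MCS, is 1 - Π P(answered ≥ minimum), with answered items binomial (m, 1 - p) and the product over the eight scales.

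| p | More than half | At least half | 1 - (1 - p)^4 |
|---|---|---|---|
| 0.2% | 0.80% | 0.002% | 0.80% |
| 0.5% | 2.02% | 0.013% | 1.99% |
| 1% | 4.08% | 0.053% | 3.94% |
| 2% | 8.32% | 0.22% | 7.76% |

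The last column is the chance that any of the four items in BP and SF is missing. It accounts for nearly all of the loss under the written rule.

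**The case against.** The strongest reply is that the appendix may not score anything. SAP 10.4.6 gives the job to vendor software and presents the appendix algorithm by example, while 18.3.3 and protocol 9.6.3.7 defer to the developers. A reader might infer that the trial will discard BP and lose PCS and MCS whenever one item is blank. The documents do not support that: the missing-data rules of the software and guideline are not in them. Even within the appendix, the SAP says only that the item stays missing; the loss of the scale and summary scores is derived from the Step 2 sum and the Step 4 formulas. This objection stands and makes the consequence conditional. It does not remove the contradiction, which lies wholly within 18.3.3.

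A reader might also cite the SF-36 compliance threshold in SAP 10.6.2 (at least 18 of 36 items) as conflicting with the more-than-half rule. It does not. It measures completion of the whole questionnaire and is not a domain scoring rule, so it is not relied on here.

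Other points limit the harm:

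- PCS and MCS are analysed with a repeated-measures model up to Week 48, so one unscorable visit does not remove a subject who has other scores.
- SF-36 is collected at both Screening and Dose 1. Under the general baseline rule in SAP 5.1, a Screening score could serve if Dose 1 is unscorable.
- A separate HRQoL SAP, not available here, may address scoring.

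No bias or material loss of precision has been shown.

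**Conclusion.** The contradiction is real and follows from SAP 18.3.3 alone: the question 8 recode for a missing question 7 has no use under the more-than-half rule. If the appendix rule is applied, one missing item in BP or SF makes PCS and MCS uncomputable for that visit. How often is unknown; the range of about 0.8% to 8% of questionnaires, against 0.002% to 0.2% under an at-least-half rule, rests entirely on the assumed rates and on independence. If the software applies another rule, the harm is an inaccurate SAP and not lost data.

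The point is minor. PCS and MCS are other secondary endpoints outside the gatekeeping sequence in SAP 10.1, so type 1 error control and the stated power figures are untouched. That at least half is the intended rule is an inference from the recode, which is why it needs confirming against the guideline.

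**What to change.** In SAP 18.3.3, Step 1, change the condition to at least half of the items answered, with the item left missing only if fewer than half are answered. The rule then agrees with the question 8 recode. Confirm the wording against the SF-36 version 2 scoring guideline and the missing-data setting of the scoring software, and state that the software/guideline rule governs.

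The cost is a few words and one check of a software setting. Relative to the rule as written, the change can only keep more visits scorable. Design, alpha and power are unaffected.
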